### 4.1 Objectives

### 4.1.1 Primary objective:

1. The mean difference of IOP in the same eye (right eye) from the baseline IOP and after the bilateral heat intervention.

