The patient will attend the clinic for three separate visits each approximately one week apart. starting with phasing 'without heat', then phasing 'with heat' and lastly phasing wearing the Blephasteam mask but with no heat as a control. The Blephasteam mask will only be used on the days of the clinic visits, the participants will not be required to use the device at home. The water carrier inserts for the masks will be designated to the same patient throughout the study for hygiene reasons. The inserts for the mask will be moistened and fitted according to the manufacturers' instructions. The wireless device will be left to reach temperature for 3-4 minutes then the patient will be asked to wear the mask and be instructed to keep their eyes closed, this occurs once at the start of each visit. The device warms the ocular surface for a set time of 10 minutes, after which the participants will remove the mask and instil their habitual Glaucoma eyedrops. They will be instructed to close their eyes and apply light pressure on the inner corner of the eye for 30 seconds. The IOP will then be measured at the first time point with the ORA and Goldman devices. Although both eyes will be treated with the heat mask only the right eve results (to eliminate bias) will be used for the statistical analysis. During the visits the patients' will have their best corrected visual acuity (BCVA) reviewed before and after measurements are taken. IOPs are measured first using the ORA tonometer (Reichert Inc., Germany) followed by the Goldman tonometer (Haag-Streit AG, Switzerland) five minutes later as per previous studies measuring IOP with the sequential use of tonometers (Tejwani et al., 2015). These IOP measures are taken at five set time points during the day called 'phasing': 08:30 +/- 30 mins, 10:30 +/- 30 mins, 12:30 +/- 30 mins, 14:30 +/- 30 mins and 16:30 +/- 30 mins. An average of three measures will be taken using the ORA machine, when using the Goldman tonometer three measures will only be taken if the first two are not within >2mmHg of each other. The procedure for the Goldman tonometer will be as follows: Two individuals (an operator and a reader) will perform the readings for the study visits. The operator will be responsible for operating the slit lamp, tonometer, and the instrument dial, while the reader will read and record the results. A full anterior segment slitlamp examination will be performed at the end of each phasing visit to ensure there are no adverse effects experienced following the treatment, including grading of the Meibomian glands (Efron scale). Additional assessments include adverse events and quality of life and ocular questionnaires.

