## Secondary analysis:

1. Adverse Events will be analysed using Chi-squared test or a summary by presenting full listing and frequencies & percentages.

2. Quality of Life (QoL) questionnaires will be analysed using normality tests, descriptive statistics and reliability tests.

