## 5.2.2 Datasets

To determine whether there is a significant change in IOP in each participant, the IOP measured with and without the addition of heat over the five time points will be used in a one-way repeat measure ANOVA test will be completed for each day of phasing. A paired ttest will be used to establish significance between an individual's IOP measure at a certain time point with or without the addition of heat. A difference of 1.5mmHg in IOP mean deviation would be considered a significant change of IOP. This value has been used in previous Glaucoma studies (Allergan Bimatoprost SR and Thea In-Sight) to provide a 95% confidence interval. A paired t-test will be used to establish any significant change in BCVA at baseline and exit visit based on a mean SD change of 0.1 logMAR or 5 ETDRS letters. Ocular safety parameters, QoL (EQ-5D-5L) and OSDI questionnaires, visual fields and slit-lamp exam measures will be summarised for the cohort by mean, standard deviation (SD), median, minimum and maximum values. A non-parametric analysis (Wilcoxon signed rank test) will be used if the data is found to not be normally distributed. Ocular adverse events and safety variables will be tabulated by whether the participant has received heat treatment or not before instilling their anti-hypotensive eye drops. Normality of the data will be checked by plotting histograms of the data (separately before and after the heat) and not using stats tests. Differences will be considered statistically significant P values less than 0.05.

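### The right-eye-only rule in Protocol section 5 is worded to cover the whole statistical analysis; it should be limited to IOP so that ocular safety measures are summarised for both heated eyes

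*Protocol*

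**What the plan says.** Section 5, within the account of the study visits, sets the eye rule: "Although both eyes will be treated with the heat mask only the right eve results (to eliminate bias) will be used for the statistical analysis" (the word printed as *eve* is evidently *eye*). The sentence just before it concerns tonometry: "The IOP will then be measured at the first time point with the ORA and Goldman devices". The sentence just after it concerns visual acuity.

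Section 4.1.1 names the right eye for one endpoint only: "The mean difference of IOP in the same eye (right eye) from the baseline IOP and after the bilateral heat intervention".

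The safety analyses name no eye:

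- Secondary analysis, section 5.2.1: "Adverse Events will be analysed using Chi-squared test or a summary by presenting full listing and frequencies & percentages".
- Section 5.2.2, adverse events and safety variables: "Ocular adverse events and safety variables will be tabulated by whether the participant has received heat treatment or not".
- Section 5.2.2, acuity: "A paired t-test will be used to establish any significant change in BCVA at baseline and exit visit".
- Section 5.2.2, fields and slit lamp: "visual fields and slit-lamp exam measures will be summarised for the cohort by mean, standard deviation (SD), median, minimum and maximum values".

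Section 7.1.1 requires POAG or OHT in both eyes, and the study title covers safety as well as efficacy.

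**The concern.** Using one eye per patient is a sound way to avoid treating two correlated eyes as independent observations when IOP is compared between visits. That reasoning does not carry over to safety. The left eye receives the same heat and is also a glaucoma or OHT eye, so it is equally exposed and equally relevant.

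Acuity, visual field indices and slit-lamp gradings are measured eye by eye. Whoever programs those summaries must decide which eyes go in. Section 5.2.2 does not say, and the one general instruction in the protocol is the right-eye rule of section 5, which is attached to the statistical analysis as a whole. If it is followed as worded, a drop in acuity, a field loss or a worse staining grade confined to the left eye would not appear in the corresponding summary. The study could then describe these measures as unchanged on the evidence of half of the treated eyes.

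**Working it through.** The protocol gives no event rate, safety precision or other figure that depends on this point, so there is no stated figure to reproduce. The check has two parts.

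**1. Scope of the rule, by type of result**

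| Result | Eye named where the analysis is described | Effect of the section 5 rule read literally |
|---|---|---|
| IOP (section 4.1.1) | Right eye | None; the two agree |
| Adverse events (sections 5.2.1 and 5.2.2) | None; full listing, tabulated by participant | Little; a left-eye event reported as an adverse event would still be listed |
| BCVA paired t-test (section 5.2.2) | None | Left eye omitted |
| Visual fields, slit-lamp measures and gradings (section 5.2.2) | None | Left eye omitted |

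The exposed part is therefore the last two rows.

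**2. Size if the literal reading is followed**

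Inputs from the protocol: 24 participants (section 7.2.1) and bilateral heat (sections 4.1.1 and 5). Heated eyes: 24 × 2 = 48. Eyes summarised: 24, which is 24/48 = 50%.

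A change confined to one eye and equally likely in either falls in the left eye with probability 0.5, and is then omitted.

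Some changes will affect both eyes, and those are caught through the right eye. Let *p* be the chance of a change in each eye and *ρ* the between-eye correlation. Neither is in the protocol; both are assumed here.

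- Both eyes affected: b = p² + ρp(1 − p)
- At least one eye affected: 2p − b
- Left eye only: p − b
- Share of affected participants omitted: (p − b)/(2p − b)

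Worked case, p = 0.05 and ρ = 0.5: b = 0.0025 + 0.5 × 0.0475 = 0.02625; at least one eye = 0.10 − 0.02625 = 0.07375; left only = 0.05 − 0.02625 = 0.02375; share = 0.02375/0.07375 = 32.2%.

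| Assumed per-eye rate | ρ = 0 | ρ = 0.5 | ρ = 1 |
|---|---|---|---|
| 2% | 49.5% | 32.9% | 0% |
| 5% | 48.7% | 32.2% | 0% |
| 10% | 47.4% | 31.0% | 0% |

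The share reaches its maximum of 50% when b = 0, that is, when changes never affect both eyes.

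**The case against.** A reader might infer that the protocol removes left-eye harm from the safety reporting altogether. The documents do not support that. Adverse events are to be listed in full with frequencies and percentages. Ocular adverse events are tabulated according to whether the participant had heat, so the participant is the unit. Section 5 also says that all data are recorded and stored for analysis, and the slit-lamp examination at each phasing visit is not limited to one eye. A left-eye finding reported as an adverse event would therefore be seen.

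The rule can also be read narrowly. It follows a sentence on IOP measurement, its stated reason of eliminating bias suits an efficacy comparison, and section 4.1.1 supports an IOP-only meaning. On that reading, section 5.2.2 is merely silent about eyes, and silence of that kind is normally settled in the statistical analysis plan, which is not at hand.

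Finally, the planned summaries are means, standard deviations, medians and extremes, plus a t-test for acuity. A single one-eyed change would show mainly in the minimum or maximum, whichever eyes are used.

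Most of this stands, and it confines the point to acuity, visual fields and slit-lamp measures. It does not remove the point. The narrow reading is possible, but the wording does not require it, and the next sentence in section 5 turns to acuity. The problem is a rule stated too broadly, not a missing detail: an analysis plan that follows it inherits the omission, and one that uses both eyes for safety departs from the protocol's words. The remark about extremes is a reason to add a count of participants who worsen.

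**Conclusion.** The point holds in a limited form. The right-eye rule in section 5 is wider than the right-eye endpoint in section 4.1.1 and makes no exception for safety. Taken literally, it leaves left-eye acuity, visual field and slit-lamp or grading results out of the section 5.2.2 summaries, although both eyes are heated and both are diseased. Adverse event reporting is much less exposed.

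On the literal reading, 24 of 48 heated eyes are summarised. The share of affected participants missed is 47% to 50% with independent eyes, 31% to 33% at a correlation of 0.5, and nil at full correlation. These shares rest on assumed per-eye rates of 2% to 10%, equal in the two eyes. Because heat is bilateral, some positive correlation is plausible, so 50% is best treated as a ceiling. The primary IOP analysis is unaffected.

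**What to change.** In section 5, limit the right-eye rule to the IOP efficacy analysis so that it matches section 4.1.1. In section 5.2.2, state that BCVA, visual field, corneal staining, conjunctival hyperaemia and Meibomian gland grading are summarised for the right and left eyes separately, and as the number of participants with worsening in either eye. The count keeps the participant as the unit and avoids treating two eyes of one person as independent.

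The cost is a sentence or two and some extra table columns. No visit or procedure is added and the primary analysis does not change. The safety tables become slightly longer, and the case report form must capture both eyes at the examinations already scheduled; this should be confirmed before data collection starts.

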## 6 STUDY SETTING

The data will be collected at the sponsor site of Hinchingbrooke and Peterborough City hospitals both part of NWAFT. The patients that will be recruited for the study will normally attend the Glaucoma clinic at this site so this will ensure continuity for them. At both hospitals an ophthalmology research team member will conduct the collection of data along with the PI. This will be a single centre pilot study that will not require any specific requirements; most of

the equipment for the study is already available within the eye clinic. The heat masks will be purchased specifically for the study from the grant awarded by Sight Research UK.

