## 8.1 Assessment and management of risk

In terms of benefits to participants, the heat masks may result in a significant and meaningful effect by reducing the IOP in combination with their ocular hypotensive eye drops. A secondary effect may be to improve any existing MGD for which the device is usually indicated. Heat therapy is the standard treatment regime for obstructive meibomian gland dysfunction (MGD). This would increase the quality of the tear film, by enhancing the meibum supply from the glands situated on the upper and lower eye lids. If clinical effectiveness is shown, the Blephasteam® would provide a non-invasive treatment option for one of the most common causes of reversible blindness (Blomdahl et al., 1997). This would also reduce the chance that patients would need to progress to dual eye drop therapy or surgical intervention.

The risks of wearing the masks are negligible; a recent study stated that the Blephasteam® device provided safe and effective warmth to the ocular area without any adverse effects on the ocular surface in this study (Purslow et al., 2010; Villani et al., 2012). Each patient will receive their own insert for the Blephasteam® device to use throughout the study to ensure there will be no cross contamination between patients.

Compliance with the heat-masks may be an issue but all site personnel will stress optimal compliance with all patients and ensure that instructions are followed by helping the patient use the device at the time of the visit.

Blephasteam ® CE certified medical device.

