#### 11. APPENDICIES

## 11.1 Appendix 2 – Schedule of Procedures

Procedures	Visits					
	Identification and consent	Visit 1- phasing without heat	Visit 2- phasing with heat	Visit 3-phasing with mask but no heat	Visit 4 – safety check	
Informed consent	x					
Demographics	x					
Medical and ocular history	х					
QoL questionnaires		x	x	X		
OSDI questionnaire		x	x	x		
Visual fields	x				x	
Drop compliance diary	x	x	x	X		
Slit-lamp examination		x	x	X		
Corneal fluorescein stain (Oxford grading)		x	x	х		
Meibomian gland dysfunction (Efron grading)		x	x	x		

HALO – PROTOCOL

			Nort	<del>h West Anglia</del>		1
Conjunctival hyperaemia (Efron grading)		х	x	HS Foundation Trust		
Application of Blephasteam®			x			
Instillation of habitual hypotensive eye drops		Х	x	x		
IOP @ 08:30 +/- 30 mins		х	x	x		
IOP @ 10:30 +/- 30 mins		х	x	x		
IOP @ 12:30 +/- 30 mins		х	x	x		
IOP @ 14:30 +/- 30 mins		х	x	x		
IOP @ 16:30 +/- 30 mins		х	x	x		
Adverse events		Х	x	х		
Far best corrected visual acuity (BCVA)		х	x	x	х	
Verification of inclusion and exclusion status	x					

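### The visit order is the same for everyone and the Goldmann operator is not masked, so observer expectation can enter the heat contrast wherever Goldmann values are analysed

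*Protocol*

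**What the plan says.** Section 5 gives one sequence for all participants: "starting with phasing 'without heat', then phasing 'with heat' and lastly phasing wearing the Blephasteam mask but with no heat as a control". The study flow chart shows the same sequence, and the schedule of procedures (Appendix 2) names each visit by its condition, for example "Visit 2- phasing with heat".

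For Goldmann tonometry, section 5 says: "Two individuals (an operator and a reader) will perform the readings for the study visits". It then divides the work: "The operator will be responsible for operating the slit lamp, tonometer, and the instrument dial, while the reader will read and record the results". The ORA is used first at each time point, as an average of three measures, and the Goldmann reading follows five minutes later.

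On staffing, section 6 says that at both hospitals "an ophthalmology research team member will conduct the collection of data along with the PI". Section 8.1 has site personnel "helping the patient use the device at the time of the visit".

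The primary outcome in section 4.1.1 is "The mean difference of IOP in the same eye (right eye) from the baseline IOP and after the bilateral heat intervention". No tonometer is named there or under the primary analysis in section 5.2.1. Section 7.2.1 says that averages from either the ORA or the Goldmann device will be analysed.

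Nothing in the protocol says that anyone is masked to condition, that the mask is handled by someone other than the operator, or that the dial is covered or reset between readings.

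**The concern.** The operator decides when the Goldmann end point is reached, which is a human judgement. The protocol states a directional expectation: section 2 predicts that heat will lower IOP further. If the operator knows which day is the heat day, small systematic differences in where the end point is set can look like a treatment effect.

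The operator and reader split does not deal with this. It separates the person who sets the end point from the person who records the value, but it does not separate the operator from knowledge of the condition.

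The study is meant as proof of concept for a larger one (sections 2 and 4.2). The protocol already tries to rule out other explanations for a fall in IOP, with a drop diary for changes in compliance and an unheated-mask visit as a control. Observer expectation is an explanation that neither of them removes. Who measures, and what they know at the time, is trial conduct that belongs in the protocol.

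**Working it through.** **Can the operator know the condition?**

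1. The order is identical for all participants (section 5, flow chart, Appendix 2), so visit number determines condition.
2. No text withholds the visit number or condition from the operator.
3. A research team member and the PI collect the data (section 6), and site personnel help with the mask (section 8.1). Nothing keeps the operator away from the mask.
4. Visits are about a week apart. An operator who meets a returning patient could work out the visit without being told.

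The operator therefore can know the condition. The protocol does not state that the operator does know.

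**Does it reach the primary outcome?** Sections 4.1.1 and 5.2.1 name no tonometer and section 7.2.1 allows either. It does if Goldmann values are used.

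**How large could the effect be?** The protocol has no figure to reproduce here. The sample of 24 rests on pilot-study references and budget, with no SD or power.

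Inputs from the protocol: n = 24 (section 7.2.1); paired t-test (section 5.2.1); p<0.05 and a 1.5 mmHg criterion (section 5.2.2). Assumed: a two-sided test, SD of the paired difference 2 to 3.5 mmHg, no true effect, and an observer shift b of 0.25, 0.5 or 1.0 mmHg.

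Formula: T is noncentral t with 23 degrees of freedom and noncentrality λ = b√24/SD; the critical value is 2.069. The smallest significant mean difference is 2.069 × SD/√24. Example: b = 0.5 and SD = 2 give λ = 0.5 × 4.899/2 = 1.225, and P(|T| > 2.069) = 21.7%.

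| SD (mmHg) | Smallest significant mean difference | p<0.05, b = 0.25 | p<0.05, b = 0.5 | p<0.05, b = 1.0 |
|---|---|---|---|---|
| 2 | 0.84 | 9.0% | 21.7% | 65.0% |
| 2.5 | 1.06 | 7.6% | 15.6% | 46.7% |
| 3 | 1.27 | 6.8% | 12.3% | 34.7% |
| 3.5 | 1.48 | 6.3% | 10.3% | 26.9% |

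Without a shift each entry would be 5%.

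**Against the 1.5 mmHg criterion.** Section 5.2.2 also treats 1.5 mmHg as the difference that matters. By normal approximation, the chance that the observed mean reaches 1.5 is P(Z > (1.5 − b)√24/SD). For b = 0.5, z = 4.899/SD = 2.45, 1.96, 1.63 and 1.40 at SD 2, 2.5, 3 and 3.5, which gives about 0.7%, 2.5%, 5% and 8%. For b = 1.0, z is half of that, which gives about 11%, 16%, 21% and 24%.

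**The case against.** The strongest case on the other side has five parts.

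- **The ORA is measured too.** It comes first at every time point, as an average of three readings, and is probably less dependent on the operator. It is not established that the primary outcome is a Goldmann reading, and the ORA values could serve as a check on a Goldmann-only shift. This stands. It limits the point to Goldmann values but does not remove it, because the protocol does not choose between the devices.
- **The shift is assumed.** This stands. No document gives an observer shift or an SD. Against the 1.5 mmHg criterion, a 0.5 mmHg shift rarely produces a positive result.
- **The procedure already gives some protection.** Someone else reads and records the value. This stands in part. A reader might infer that the number is hidden from the operator, but the operator turns the dial and nothing says that it is covered.
- **Masking is harder than it looks.** A reader might infer that the two people named are enough to mask the operator. By headcount they are, but under a fixed order an operator who sees a returning patient can deduce the condition. Concealment must also last from the first reading to the one at 16:30, with a patient who knows. This stands, and it makes varying the order part of the remedy.
- **The unheated-mask visit keeps its use.** A reader might infer that the control is worthless without masking. It is not: it still controls for wearing the mask and for the rest period. What it cannot control is observer expectation.

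The modest scale of the study (24 patients, limited budget) weighs against costly remedies. It does not weigh against one that needs no extra staff or visits.

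**Conclusion.** The point holds in a limited form. One fixed order and no masking of the Goldmann operator leave a judgement-based reading open to expectation bias, in the direction of the study hypothesis. The bias reaches the primary outcome if Goldmann values are used, which the protocol permits.

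That staff can know the condition is a strong inference from the fixed order and the absence of masking; the protocol does not say that they know it.

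The percentages show sensitivity and do not estimate this trial's false-positive rate. Under the assumed SDs, a shift of 0.25 mmHg barely matters (9 to 6% instead of 5%), 0.5 mmHg gives 22 to 10%, and 1.0 mmHg gives 65 to 27%. No figure in the protocol is shown to be wrong.

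The change is worth making because it is cheap and the result is meant to justify a larger study.

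**What to change.** In section 5, state that:

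- the reader, not the operator, fits the mask, switches it on or leaves it off, and removes it;
- the operator is absent until the mask is off, is not told the visit number or condition, and sees neither the dial value nor earlier readings;
- the order of the heated-mask and unheated-mask visits is varied by a random list held by the reader, because masking is not credible under a fixed order;
- the heated versus unheated mask comparison is reported as the one protected from observer bias.

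Bring the flow chart and Appendix 2 into line, and name the primary tonometer in section 4.1.1 so that it is clear whether the primary result depends on Goldmann readings. If a site cannot keep the masking, state this as a limitation.

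Cost: protocol wording, a random list and a room rota, within the two staff named and with no added visit or procedure. The operator must stay away during warm-up and wear (3 to 4 plus 10 minutes, so about 14) and from tasks that reveal the condition for the rest of the day. Some gaps remain: the no-mask visit and the patient cannot be masked, the patient may reveal the condition, and the reader stays unmasked.

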#### **STUDY FLOW CHART**

Suitable patients identified and consented from Glaucoma clinics at HH and PCH-visual fields test completed One week prior to the first phasing visit the patient will be asked to start completing their drop compliance diary, continued for the duration of the study IOP phasing for POAG/OHT patients on topical therapy WITHOUT heat (no mask) - first visit IOP phasing for POAG/OHT patients on topical therapy WITH heat - second visit IOP phasing for POAG/OHT patients on topical therapy WITHOUT heat (wearing mask) third visit One to two weeks after completing the study a further visual fields test will be completed safety visit including a visual fields test and visual acuity measure Patient continues with their normal Glaucoma care

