
One to two weeks after completion of the study the patients will undergo a further visual

fields test (Humphrey sita fast 24-2) to ensure no significant progression of their disease has occurred as a result of the study regime. All data will be recorded and stored for analysis at the end of the trial and made available to the standard of care treating clinician. At the end of the trial the patients will continue their Glaucoma visit schedule as requested by their treating Ophthalmologist.

All attempts will be made to have participants complete the study by organising visits that fit in with their timetable and offering further appointments should the participant not be able to attend on a certain day. Participants will be offered reimbursement for travel and refreshments on the day of their study visits. In the case of participant 'drop-outs', the research team will attempt to recruit further participants otherwise patients on whom all the tests could not be performed will be excluded from analysis.

When designing this trial, it was important for us to ensure that the comments and suggestions of the public and patients were taken on board, so that we could confirm that this trial was suitable for people with POAG or OHT. To do this, a patient and public involvement (PPI) forum was be organised on 30th May 2023 and the trial subsequently developed with the help of people diagnosed with Glaucoma in the Cambridgeshire area who agreed that the tests and procedures included in this study were practical and acceptable to patients.

It is the intention of the research team that the results of the study will be disseminated in peer-reviewed articles and at ophthalmic conferences.

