## 7.3.2 Consent

Patient information leaflets and consent forms will be designed so that the patient can understand the purpose and nature of the research. Individuals will be supplied with as much information as they require in order to make an informed decision about participation in this study including what the research involves, its benefits (or lack thereof) and any risks and burdens. It will be made clear that the decision whether or not to participate will not affect any on-going or future treatment within each trust. It will be made clear that participation is voluntary and that they can withdraw at any time and for any reason. They will be assured that confidentiality will be maintained at all times.

Having agreed to participate in the study, informed consent will be received from the patient by the PI prior to the patient entering into the screening phase. The patient will be given the opportunity to ask questions and these will be recorded along with answers.

They will then undergo a screening assessment, where, if eligible, they will then be booked in for continuation of the study.

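### The visual-field and acuity safety check is timed from study completion, so a participant who has the heat and withdraws before visit 3 has no planned post-heat field test or later acuity check

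*Protocol*

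**What the plan says.** The order of visits is fixed: phasing without heat, phasing with heat, then phasing with the unheated mask, about a week apart (Protocol section 5). Heat is therefore given once, at visit 2.

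On the closing safety check, section 5 states "One to two weeks after completion of the study the patients will undergo a further visual" fields test, "to ensure no significant progression of their disease has occurred as a result of the study regime". The flow chart agrees: "One to two weeks after completing the study a further visual fields test will be completed", described as a "safety visit including a visual fields test and visual acuity measure". The schedule of procedures (section 11.1) marks visual fields at consent and at visit 4 only.

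On the heat day itself the protocol does look for harm. Section 5 says: "A full anterior segment slitlamp examination will be performed at the end of each phasing visit to ensure there are no adverse effects experienced". It also has "best corrected visual acuity (BCVA) reviewed before and after measurements are taken", together with adverse-event assessment. The schedule confirms slit lamp, corneal staining, Meibomian and hyperaemia grading, adverse events and BCVA at visit 2.

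Section 7.3.2 says participants will be told that "they can withdraw at any time and for any reason". For drop-outs, section 5 says the team will try to recruit others, and that patients without all the tests are otherwise left out of the analysis. Section 5.2.2 plans a paired t-test of any "significant change in BCVA at baseline and exit visit".

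**The concern.** Exposure to heat creates the need for the closing check, but what triggers the check is finishing all three phasing visits. The two separate for anyone who leaves between visit 2 and visit 3. That person has been exposed, is free to go, and has no stated route to visit 4.

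The study title includes safety, the exclusion criteria in section 7.1.2 recognise that participation could worsen the visual field, and section 5 gives detection of progression as the reason for the final field test. If the test is done only in people who attended everything, the exit field and acuity summaries describe those who tolerated the regime. Should any withdrawal be related to harm, the summaries would lean towards showing none. A choice of analysis set made later cannot repair this, because the measurement would not exist.

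**Working it through.** The protocol gives no figure on this point to reproduce. The check is a comparison of what is scheduled after heat for two kinds of participant, from section 5, the flow chart and the schedule of procedures. It assumes the leaver stays to the end of visit 2.

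| Assessment after heat | Completes all visits | Leaves after visit 2 |
|---|---|---|
| Slit lamp, staining, grading on the heat day | Yes | Yes |
| BCVA on the heat day | Yes | Yes |
| Adverse events on the heat day | Yes | Yes |
| Slit lamp and adverse events at visit 3 | Yes | No |
| Later BCVA (visits 3 and 4) | Yes | No |
| Visual field (visit 4) | Yes | No |

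**Does completion cover people who stop early?** Section 5 speaks of efforts to have participants complete the study and then deals separately with drop-outs. In that text a drop-out is someone who has not completed. No section describes an assessment at withdrawal.

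**What happens to the leaver's data?** The paired acuity test needs a baseline and an exit value, and a leaver has no exit value. Under section 5 the leaver may be replaced, and the exclusion of patients without all tests makes no exception for safety data. An exit table could then show 24 results with no sign that someone exposed to heat is absent from it.

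**How many people?** No dropout rate is stated, so this is an assumption with a range. If 5% to 20% of 24 left between visits 2 and 3:

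- 0.05 × 24 = 1.2 and 0.20 × 24 = 4.8, so about 1 to 5 people.
- Without replacement, the share of heat-exposed participants with no exit check is 1/24 = 4.2% to 5/24 = 20.8%.
- If each leaver is replaced by someone who completes, the number exposed rises to 25 to 29, and the share is 1/25 = 4.0% to 5/29 = 17.2%.

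**The case against.** The strongest reply is that a reader might infer that such a participant is never checked for harm, and that this is untrue. It is untrue. Heat is applied at the start of visit 2, pressures are followed to about 16:30, and the visit ends with a slit-lamp examination, with BCVA and adverse events also recorded. Routine glaucoma care continues (section 8, General), and study data go to the treating clinician. The gap is limited to the visual field and to anything that appears after the participant goes home.

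Second, the timing phrases can be read as describing the normal sequence, not as a condition. The schedule lists visit 4 without mentioning completion, and nothing forbids offering it to someone who stopped early. This stands in part: the protocol is silent and does not prohibit it. But staff who follow the flow chart and section 5 have no instruction to book the visit, and section 5 sets drop-outs apart from those who complete.

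Third, a reader might put a rate on missed harm, for example one true loss among four leavers, reported as 0/20 when the truth is 1/24 (4.2%). The documents do not support that contrast. Both the dropout and the event are invented, and replacing the four leavers would change it to 0/24 against 1/28 (3.6%). Nor do the documents show that leavers are likelier to have been harmed: withdrawal may be for any reason, and section 8.1 calls the risks of wearing the masks negligible.

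**Conclusion.** The point holds in a limited form. Followed as written, the plan leaves a participant who has heat and withdraws before visit 3 with same-day checks only: no post-heat visual field, no later acuity and no later adverse-event enquiry. Combined with replacement and the all-tests exclusion in section 5, exit safety results would describe completers.

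The size cannot be derived from the documents. The range of about 1 to 5 people rests wholly on the assumed 5% to 20% loss after heat, and the direction of any bias depends on whether withdrawals relate to harm, which is unknown. The gap is worth closing because the protocol itself treats the field test as necessary and the correction is cheap. In a 24-person study with a single ten-minute heat exposure it does not threaten the design.

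**What to change.** In the flow chart and section 5, state that every participant who received the heated mask is offered visit 4, with the tests already listed for it, one to two weeks after the last phasing visit attended, whether or not all phasing visits were completed, unless they decline.

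In section 5, limit the exclusion of patients without all tests to the IOP efficacy analysis. Safety summaries should include everyone who received heat and report how many have no exit assessment. Without this second change, the added data could still be discarded.

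Two details follow. The schedule marks no adverse-event enquiry at visit 4, so re-timing the visit restores the field and acuity checks but not that enquiry; the team should say whether it will be made when visit 4 is offered. Also, a completer is tested about two to three weeks after heat (one week to visit 3, then one to two more), but someone who left after visit 2 would be tested at one to two weeks, so the interval since heat should be reported.

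The cost is a little staff time and expenses of at most £20 + £15 = £35 per withdrawn participant (section 7.3.1). If drop-outs are replaced, the number of visit 4 appointments may exceed 24.
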